14.0 STUDY VARIABLES

Variable	Operational definition	Variable type	Unit of measurement
Outcome variables			
Percentage of water consumed	Average consumption of water/average consumption of total liquids	Numeric/continuous	%
Total liquid Consumption	Average amount of total liquids consumed per child over a 3-day period	Numeric/continuous	mL
Water consumption	Average amount of water consumed per child over a 3-day period	Numeric/continuous	mL
Effectiveness of educational strategy	Increase in the percentage of water consumed, 1 year after completing the interventions within each group relative to baseline	Qualitative/dichotomous	1: yes 2: no
Secondary variables			
Age	Years old at the beginning of the school year	Numeric/continuous	Years
Gender	The sex indicated on each child's birth certificate	Qualitative/dichotomous	1: male 2: female
BMI	Indicator of the relationship between weight and height	Numeric/continuous	kg/m ²
Health condition	Health condition that (in the opinion of the investigator) enables the participant to have free consumption of water	Qualitative/dichotomous	1: healthy 2: sick
Water consumption per school	Quantity of water consumed in 1 month per participating school	Numeric/continuous	L

Operational Definitions

Educative intervention: Number of times that a student will receive the educational strategy for each elementary school year that they attend

Educational strategy: Set of activities aimed at teaching the importance of hydrating with water and promoting its consumption to maintain one's health (Appendix I)

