7.2 Secondary Objective

This study seeks to compare the monthly water consumption of participating schools during the follow-up period.

This study seeks to describe the annual body mass index (BMI) of the participating students during the follow-up period.

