12.4 Intervention

At all participating schools, the principal investigator will conduct an approximately 1-hour briefing for parents to 1) explain the study's operational generalities and answer all questions and 2) provide instructions for completing the beverage consumption survey. Subsequently, the 3-day baseline record of beverage consumption will be collected.

At the beginning of the school year, first grade teachers will be trained by a nutritionist (one per school) to dispense the educational sessions (Appendix VI, VII, VIII), and the manual and materials for both teachers and students will be delivered.

The students will receive four educational sessions of approximately 1 hour. These sessions will be given every 2 weeks, and some will be supervised by a nutritionist.

The four schools will be assigned to one of the following three groups based on school enrollment and the interest of the teachers in participating:

Students in Group I will receive the education strategy only during the first grade; students in Group II will receive the educational strategy during first and second grades; and students in Group III will receive the educational strategy during first, second, and third grades.

	1st grade	2nd grade	3rd grade
Group I	X		
Group II	X	X	
Group III	X	X	X

With the delivery of the first educational session, free access to water will be initiated through Welltek water dispensers, model WT-POU-300 A (approved and certified by Cofepris and the National Institute of Physical Educational Infrastructure; INIFED), installed inside the classrooms. Children will also receive a reusable 600-mL bottle (twice) so that they may consume water throughout the day. The availability of water will be guaranteed during four school cycles.

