13.0 SAMPLE SIZE

Considering the results of the previous study where a mean difference of 80.74 mL was found with regard to water consumption with an SD of 399 mL as well as considering an α of 0.05 and a β of 0.1, we used the following formula to calculate a significant difference in means

$$n = [(Z_{1-\alpha} + Z_{1-\beta})^2 * s^2] / d^2$$
$$[(1.96 + 1.28)^2 * 399^2] / 80.74^2 = 256.36$$

N = 257 children

The sample should include 329 first graders (allowing for a 28% loss margin) who will attend the 2017-2018 school year. This sample represents all of the four intervention schools that participated in the previous study.

2016-2017 school enrollment of the intervention schools participating in the previous study

School	Health Center	First grade	Total	Second grade	Total	Third grade	Total	Total school enrollment
Ramón Durand	Ajusco	32 32	64	31 32	63	26 27	53	341
Xitle	Ajusco	27 29 25	81	28 27 29	84	31 30 29	90	529
Guillén de Lampart	Santa Úrsula	28 26 27	81	31 32 30	93	27 27	54	475
Tlamatini	Santa Úrsula	34 35 34	103	36 37 36	101	33 33 33	99	600
			329		278		243	1,604

	Group I	Xitle	81
	Group II	Guillén de Lampart	81
	Group III	Ramón Durand Tlamatini	167

Based on the school enrollment of the current school year (2016-2017), schools with the same number of first graders will be assigned to Groups I and II. For Group III, the schools with the highest and lowest enrollments will be added.

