15.0 STATISTICAL ANALYSIS

The analysis will be performed using the IBM SPSS version 22.0, and non-parametric statistics will be used.

Baseline measurement of beverage consumption (Time 1). The basal consumption of the different beverage categories will be summarized using medians, minimums, and maximums. We will apply the Kruskal-Wallis test (K of independent samples) to compare the differences in baseline beverage consumption among the three groups.

Baseline measurement and at the end of the interventions (Times 1 and 3). The percentage of water consumed at baseline will be compared with that 1 year after finishing the intervention for each group using the Wilcoxon test.

Comparison among the three groups. The percentage of water consumed will be compared among the three groups 1 year after the intervention is completed using Friedman's test of related samples.

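### Monthly water use is compared between schools in total litres with no per-pupil or per-school-day denominator, so the comparison mixes enrolment with drinking

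*Combined protocol and SAP*

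**What the plan says.** Section 7.2 sets as a secondary objective to "compare the monthly water consumption of participating schools during the follow-up period". Section 14.0 lists the matching variable, water consumption per school, as "Quantity of water consumed in 1 month per participating school", with litres as the unit. The same table gives the child-level water variable a denominator: "Average amount of water consumed per child over a 3-day period".

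Section 15.0 covers the beverage records only. Its between-group comparison reads "The percentage of water consumed will be compared among the three groups 1 year after the intervention is completed using Friedman's test of related samples". It contains no analysis of monthly school litres, so no adjustment for school size enters there.

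Section 12.4 assigns schools "based on school enrollment and the interest of the teachers in participating". The enrolment table in Section 13.0 shows one school each in Groups I and II and two in Group III: "For Group III, the schools with the highest and lowest enrollments will be added". Section 12.4 places dispensers inside classrooms and guarantees water for four school cycles. It does not say whether every classroom is served, which ones count toward the school total, or how the litres are recorded.

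**The concern.** A school's total litres are the product of how many children drink, how much each one drinks and how many days the school is open. The objective is of interest only for the second factor. As defined, the variable reports all three together, and the first differs substantially between these schools.

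A reader who sees one school use far more water than another will tend to take this as a difference in drinking behaviour. In raw litres it may be partly or wholly a difference in enrolment, and a school whose children drink more each can rank below one whose children drink less. The widest size gap lies between the two Group III schools, which receive the same number of rounds of the strategy.

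**Working it through.** **Inputs** (Section 13.0 enrolment table, 2016-2017)

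| School | First grade | Grades 1-3, as tabulated | Whole school |
|---|---|---|---|
| Group III, smaller | 64 | 64+63+53 = 180 | 341 |
| Group II | 81 | 81+93+54 = 228 | 475 |
| Group I | 81 | 81+84+90 = 255 | 529 |
| Group III, larger | 103 | 103+101+99 = 303 | 600 |

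**The plan's own totals.** The plan gives no figure for monthly school water, so the enrolments are what can be checked.
- First grade: 64+81+81+103 = 329, as stated.
- Whole school: 341+475+529+600 = 1,945, but the table states 1,604. The difference is 341, so the smallest school was left out.
- Second grade: 63+84+93+101 = 341, stated as 278. Third grade: 53+90+54+99 = 296, stated as 243. Both stated totals omit the same school.
- In the largest school, the second-grade classes 36+37+36 give 109, stated as 101.

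The ratios below use the individual school figures, not these totals.

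**Formula.** Monthly litres = N × q × D, where N is the number of pupils counted, q the litres per pupil per school day and D the school days in the month. With q and D equal at two schools, the ratio of litres is the ratio of N.

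**Result with identical drinking, largest school against smallest**
- Whole school: 600/341 = 1.76
- Grades 1-3: 303/180 = 1.68
- First grade only: 103/64 = 1.61

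Group I school against Group II school:
- Whole school: 529/475 = 1.11
- First grade only: 81/81 = 1.00

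To match the largest school's litres, pupils at the smallest would each have to drink 76% more (600/341 − 1), or 61% more on first graders (103/64 − 1).

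**Illustration.** The documents give no intake at school, so assume 0.1 to 0.6 L per pupil per day and 20 school days.
- At 0.1 L: 341×0.1×20 = 682 L against 600×0.1×20 = 1,200 L.
- At 0.6 L: 341×0.6×20 = 4,092 L against 600×0.6×20 = 7,200 L.
- The ratio is 1.76 throughout, whatever intake is assumed.
- A reversed ranking: if pupils drink 0.3 L at the smallest school and 0.2 L at the largest, the totals are 341×0.3×20 = 2,046 L and 600×0.2×20 = 2,400 L. The school with 50% higher intake per pupil shows fewer litres.

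**After the fix.** Dividing by N × D returns q. Equal drinking then gives a ratio of 1.00, and the last example gives 0.3 against 0.2, in the right order.

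**The case against.** The best defence is that Section 7.2 does not say how schools are to be compared. Month-to-month trends shown school by school would be largely free of school size, and with no analysis in Section 15.0 no faulty test has been prescribed. That is a fair reading of what the objective could become. But its wording compares schools, the only definition supplied is total litres, and no within-school analysis is named. Trends would also still vary with the number of school days in each month.

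Second, the allocation partly balances size. Groups I and II have 81 first graders each, and the two Group III schools average (64+103)/2 = 83.5. Mean whole-school enrolment is 529, 475 and (341+600)/2 = 470.5, a spread of 529/470.5 = 1.12. This stands, and it limits the size effect if group means per school are shown. It does not help a school-by-school comparison, where both Group III schools differ in size from the others and from each other on either count.

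Third, the objective is secondary and has no stated hypothesis, and litres could be divided by enrolment at reporting. That is so. It makes the repair easy, but it does not make the written definition suitable.

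Some stronger readings are tempting but not supported:
- **That size alone would produce whatever differences appear.** The enrolments show that size is sufficient for a gap, not that it is the only source.
- **That Group III would show 167/81 = 2.06 times the litres of Group I or II.** This needs litres summed by group, which is planned nowhere. The adding of schools in Section 13.0 concerns allocation.
- **That this is the trial's only measure independent of parents' reports.** Section 12.5 has weight, height and body composition measured by instrument. School litres are at most the only such measure of drinking, and their recording method is not described.

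**Conclusion.** The point holds for a between-school comparison in raw litres. The stated definition has no denominator, and with equal intake per child and equal school days it would put the largest school at 1.76 times the smallest on whole-school enrolment, or 1.61 times on first graders. Which figure applies depends on which classrooms count, and the plan does not say.

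The figures assume that 2016-2017 enrolments approximate those of the follow-up years, which run to June 2021, and that all counted pupils have access to the water. The definition should be changed, but the consequence is confined to one secondary objective.

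A reader might infer that per-pupil litres would validate the parent-recorded percentage of water. They would not: that outcome divides water by all liquids and comes from a journal completed at home that includes a weekend day, whereas school litres contain neither other beverages nor intake outside school. Nor would the per-pupil scale isolate the effect of more rounds. With one school each in Groups I and II, number of rounds cannot be separated from school.

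**What to change.** - **Section 14.0:** define the variable as litres per enrolled pupil in the classrooms served by the dispensers, per school day in the month. State which classrooms count and how the litres are recorded.
- **Section 7.2:** make the comparison on that scale, and keep total litres as a descriptive column.
- **Section 15.0:** add a short entry for this objective, for example a descriptive table or plot by school and month. Describe the measure as a supplementary indicator of drinking at school.

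**Cost.** A few lines of protocol text, plus enrolment for the counted classrooms and school-day counts, to be obtained from school records for each follow-up year. The documents give enrolment for 2016-2017 only and contain no school calendar. The Section 13.0 table should be corrected before its figures serve as denominators: the whole-school, second-grade and third-grade totals each omit the smallest school, and one second-grade entry disagrees with its own classes. No child-level data collection changes.

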15.0 STATISTICAL ANALYSIS

The analysis will be performed using the IBM SPSS version 22.0, and non-parametric statistics will be used.

Baseline measurement of beverage consumption (Time 1). The basal consumption of the different beverage categories will be summarized using medians, minimums, and maximums. We will apply the Kruskal-Wallis test (K of independent samples) to compare the differences in baseline beverage consumption among the three groups.

Baseline measurement and at the end of the interventions (Times 1 and 3). The percentage of water consumed at baseline will be compared with that 1 year after finishing the intervention for each group using the Wilcoxon test.

Comparison among the three groups. The percentage of water consumed will be compared among the three groups 1 year after the intervention is completed using Friedman's test of related samples.

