12.5 Evaluation Process

In September 2017, the medical examination of the students and the process of inclusion will be performed; instructions will be sent to parents, and teacher training will be conducted. During October 2017, the baseline record regarding the consumption of beverages will be collected (Time 1). The educational sessions will be given from November 2017 to January 2018. A second record (Time 2) will be obtained at the end of the interventions in each group (end of June), and a third record (Time 3) will be obtained from each group 1 year after completing the interventions (end of June).

Baseline		End of 1st grade	End of 2nd grade	End of 3rd grade	End of 4th grade
Group I	X	X	X		
Group II	X	X		X	
Group III	X	X			X

 Evaluation 1 year after completing the number of interventions associated with each group

In addition to measurements at baseline and at each evaluation time, body weight will be measured, and lean mass, fat free mass, fat percentage, total body water, and BMI will be analyzed using a body composition analyzer via electrical bioimpedance (TANITA TBF-310 GS). Height will be measured using a portable stadiometer (dry mark, model 213, Hambur Germany). Participants will be measured in light clothing (T-shirt and sport shorts) and without shoes. A nutritionist will be calibrated to perform the measurements. BMI will be classified using the WHO values standardized by age and gender.

The following table summarizes the procedures to be performed throughout the trial.

Procedure	Sep 2017	Jun 2018	Sep 2018	Jun 2019	Sep 2019	Jun 2020	Sep 2020	Jun 2021
School medical examination	X							
Weight, size, and body composition measurements	X	X		X		X		X
Instructions for completing the daily beverage record	X	X		X		X		X
Teacher training	X		X		X			
Daily beverage record	X	X		X		X		X
Group I intervention	X							
Group II Intervention	X							
Group III Intervention	X							

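### The three-group comparison uses Time 3 alone, so school differences in starting level and in response to the shared first year stay in it

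*Combined protocol and SAP*

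**What the plan says.** Section 15.0 plans three analyses: a Kruskal-Wallis test of baseline beverage intake; a within-group Wilcoxon test ("The percentage of water consumed at baseline will be compared with that 1 year after finishing the intervention for each group"); and a comparison among groups by Friedman's test ("The percentage of water consumed will be compared among the three groups 1 year after the intervention is completed"). The effectiveness variable in 14.0 is also defined against baseline. No analysis uses a record taken between baseline and Time 3.

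Under 12.4 every group has the strategy in first grade, and all schools get dispensers and bottles. "Students in Group I will receive the education strategy only during the first grade"; Groups II and III continue into second grade, and Group III into third. The first-grade sessions run from November 2017 to January 2018, with no distinction by group (12.5), so the groups first differ in second grade. Section 13.0 puts one school in Group I (81 children), one in Group II (81) and two in Group III (167). Section 12.4 assigns them by enrolment and teacher interest.

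The grid in 12.5 marks an end-of-first-grade record for all three groups, and the procedures table lists a beverage record in June 2018. The sentence in 12.5 that defines Time 2, like the Summary in 1.0, instead ties the second record to the end of each group's own interventions. That is June 2018 only for Group I.

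**The concern.** The question is one, two or three interventions. Whatever separates the schools by June 2018 cannot be due to the number of interventions, because by then all have had one. Two such differences can reach Time 3: the level at which each school started, and how well it took to the dispensers, bottles and first course. A comparison of Time 3 values with no earlier record leaves both in place. With one school each in Groups I and II, they look exactly like a group effect.

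The shared response may not be small. In the earlier study (4.5.2), which supplied the four schools invited here (12.3), the intervention group's median water intake rose 167 mL over eight months. That is 167/80.74 = 2.07 times the planning difference in 13.0, although a median and a mean are not strictly comparable. The documents do not say how far schools differed in that response.

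The plan also forgoes a check that its design offers. From October 2017 to June 2018 the four schools have the same treatment, so the spread of their changes shows how far schools differ for other reasons.

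**Working it through.** **The plan's own figures.** The plan states no figure on this point. Its sample size reproduces: (1.96 + 1.28)² × 399² / 80.74² = 256.36, hence "N = 257 children". That formula has no between-school term, so school variation below is assumed.

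**Time scale.** October 2017 to Time 3 is 20, 32 and 44 months in Groups I, II and III. June 2018 to Time 3 is 12, 24 and 36 months.

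**Inputs.**
- From the documents: completers at 72% of enrolment (28% loss). 81 × 0.72 = 58 in each of Groups I and II; 64 × 0.72 = 46 and 103 × 0.72 = 74 in the two Group III schools.
- Assumed: child SD 18 percentage points; correlation r = 0.5 between any two records; school SDs of 3 points for level (L), 3 for first-year response (A) and 1 for later drift (D); no true effect of the number of interventions.
- A fraction p of A persists to Time 3. The documents do not give p, so p = 1, 0.5 and 0 are all shown.

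**School difference left in each analysis.** With two covariates at r = 0.5, each coefficient is r/(1 + r) = 1/3, and the residual variance fraction is 1 − 2r²/(1 + r) = 0.67, so the child SD becomes 18 × √0.667 = 14.7. A change score keeps child SD 18 × √(2(1 − r)) = 18.

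| Analysis | School term left | School SD, p = 1 / 0.5 / 0 | Divided by child SD |
|---|---|---|---|
| Time 3 alone | L + pA + D | 4.36 / 3.50 / 3.16 | 0.24 / 0.19 / 0.18 |
| Adjusted for both records | L/3 + (p − 1/3)A + D | 2.45 / 1.50 / 1.73 | 0.17 / 0.10 / 0.12 |
| Change from October 2017 | pA + D | 3.16 / 1.80 / 1.00 | 0.18 / 0.10 / 0.06 |
| Change from June 2018 | (p − 1)A + D | 1.00 / 1.80 / 3.16 | 0.06 / 0.10 / 0.18 |

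For example, Time 3 alone at p = 1 is √(9 + 9 + 1) = 4.36; the adjusted analysis is √(1 + 4 + 1) = 2.45.

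**Simulated rejection at nominal 5%.** Kruskal-Wallis is used for the unadjusted and change-score rows, because Friedman's test is for related samples and the groups are independent. The adjusted row is an analysis of covariance.

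| Analysis | p = 1 | p = 0.5 | p = 0 |
|---|---|---|---|
| Time 3 alone | 51% | 37% | 33% |
| Adjusted for both records | 33% | 15% | 16% |
| Change from October 2017 | 36% | 14–15% | 7% |
| Change from June 2018 | 7% | 14–15% | 32% |

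Runs differ by a few points; the adjusted analysis at p = 1 gave 29% to 33%. With no school variation every analysis rejects at about 5%.

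**Range at p = 1.** With first-year SD 5, Time 3 alone rejects in 65% and the adjusted analysis in 50%. With drift SD 2 the figures are 52% and 41%.

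**Precision of the school-level check.** A difference in first-year change between two schools of 58 has a standard error from child sampling of 18 × √(1/58 + 1/58) = 3.3 points. For the two Group III schools it is 18 × √(1/46 + 1/74) = 3.4.

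**The case against.** The strongest objection is that the root problem is one school each in Groups I and II, assigned by enrolment and teacher interest, and that no reference record cures it. That is right, and it limits what the fix can claim.

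Second, the adjusted analysis does little better than change from October 2017 when the response persists (about 33% against 36%), and does worse when it fades (16% against 7%). That also stands. But no three-group test of change from October 2017 is planned. Against the comparison that is planned, adjustment rejects less often in every scenario above. It also leaves a residual variance of 0.67, against 1.00 for a change score at r = 0.5.

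Three stronger readings are tempting, and the documents support none of them.
- A reader might infer that the group comparison is measured from October 2017. Only the within-group Wilcoxon test and the effectiveness variable are; the comparison among groups uses no reference record.
- A reader might infer that change from June 2018 removes the problem at no cost. Its 7% holds only if the first-year response persists fully and later drift is small. If the response fades, that score over-corrects and rejects in 32%. Whether the change lasts is what the trial asks (5.0).
- A reader might want a rule that a Time 3 gap larger than the first-year gaps counts as an effect. Such a cutoff has no error rate, and the 3.3-point standard error exceeds the assumed school SD of 3.

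**Conclusion.** The point holds in a limited form. The planned three-group comparison ignores the October 2017 record and the June 2018 record that the 12.5 tables schedule. It therefore keeps school differences that arose before the groups were treated differently. Under the base assumptions, using both records lowers false positives from about 51%, 37% and 33% to about 33%, 15% and 16% at full, half and no persistence.

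The absolute rates rest on assumed school SDs, child SD and correlation, and should not be read as estimates for these schools. In every scenario shown with school variation, the adjusted analysis rejects less often than the planned one. The rates stay above 5%: the confounding of school with group, non-random assignment, later drift and unequal follow-up (12, 24 and 36 months from June 2018) all remain. Conclusions about the number of interventions need that limit stated beside them.

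**What to change.** 1. In 15.0, adjust the three-group Time 3 comparison for each child's October 2017 and June 2018 percentages, using a method for independent groups. Report change from October 2017 and change from June 2018 as sensitivity analyses; neither should stand alone.
2. Report the October 2017 to June 2018 change for each of the four schools with confidence intervals, showing the two Group III schools separately. Present it as a descriptive negative control, with no attribution cutoff.
3. Reconcile the Time 2 sentence in 12.5, and the matching sentence in the Summary, with the 12.5 grid and procedures table, so that the June 2018 record is confirmed in all three groups.
4. State in 15.0 that school and group cannot be separated in Groups I and II, and word the conclusions accordingly.

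The cost is revised wording, a few extra tables and a rule for children without a June 2018 journal. That rule should say whether the elimination criterion in 11.3 on incomplete records applies to them. If the tables in 12.5 are followed, no extra data collection is needed. If the Time 2 sentence has been followed instead, the June 2018 record may exist only for Group I, and the adjustment could then use October 2017 alone.

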Material and methods. A community intervention trial will be conducted at four public elementary schools of the Coyoacán Delegation in Mexico City. It will include healthy first graders during the 2017-2018 school year whose parents agree to participate through verbal informed consent and a signed privacy notice. These parents will complete a baseline 3-day beverage record (two weekdays and one weekend day). The four schools will be assigned to one of three groups: Group I will receive the educational strategy during the first grade; Group II will receive it during first and second grades; and Group III will receive it during the first, second, and third grades. All schools will have water dispensers inside the classrooms, and the children will receive a reusable 600-mL bottle so they are able to consume water on demand throughout the day. A second record of beverage consumption will be obtained by completing multiple interventions within each group, and a third record will be completed 1 year later.

Statistical analyses. Descriptive statistics will be used to summarize the numerical variables with medians, minimums, and maximums. The Kruskal-Wallis test will be applied to compare the baseline intake of beverages among the three groups. In each group, baseline water consumption will be compared with that 1 year after the end of the interventions using the Wilcoxon test.

Ethical Considerations. This research is considered to have minimal risk; thus, the Research Ethics Committee will be asked to approve a request for verbal informed consent, and the parents will be asked to sign a privacy notice. The general health law for research in Mexico will be respected, and ethical clinical practices will be followed. The authors have no conflicts of interest to declare.

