4.5.2 Effectiveness of the educational strategy “I Prefer Plain Water”

A previous study evaluated the effectiveness of the educational strategy to increase water consumption of first, second, and third graders in Mexico City. For this purpose, a community intervention test was conducted across eight elementary schools in the Coyoacán Delegation during the 2014-2015 school year. A 3-day beverage consumption record (two weekdays and one weekend day) was obtained from all participants. All schools were provided with water bottles inside the classrooms, and the children received a reusable 600-mL bottle. The schools were randomly assigned to an educational intervention group (IG) or a control group (CG). The IG had the educational strategy applied. At the end of the educational session cycle 4 months after baseline, a second record of beverage consumption was obtained, and a third was obtained at the end of the school year (4 months after the second). The strategy was considered effective if the students increased their water consumption by more than 220 mL.

For the analysis, 777 of the 1,105 children included were considered: 413/986 in the IG and 364/762 in the CG with a median age of 7.1 years (range 5.6 to 9.4 years). The children for whom the record of drinks was obtained at all three times were analyzed. From the baseline record to the end (8 months), the IG median increase in water consumption was 167 mL ($P < 0.001$) compared with the CG, which increased 37 mL. The educational strategy was effective for 166/413 of the children in the IG compared with 95/364 of the children in the CG ($P < 0.001$). The IG showed an 80 mL increase in their median total liquid consumption from baseline to first record and a 41 mL increase from the baseline record to the final record. In comparison, the CG increased 33 and 38 mL, respectively. These changes were not significant between the two groups but were significant within the IG from baseline to the first record. Significant differences were found with regard to the consumption of sugary beverages between groups ($P = 0.027$). The IG decreased 42 mL (16.8%), and the CG decreased 36 mL (14.6%) from baseline to the final record. Regarding the consumption of soft drinks, the IG decreased the consumption from 41 mL to 0 mL, whereas the CG reduced from 83 to 33 mL from baseline to the final record ($P < 0.001$). Figure 1 shows the change in beverage consumption in the groups at all three times.

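### The effectiveness definition and the per-group Wilcoxon tests cannot attribute change to the education, and with groups of 81/81/167 the same change reaches significance more often in Group III

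*Combined protocol and SAP*

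**What the plan says.** Section 14.0 lists the effectiveness of the educational strategy as a yes/no outcome, defined as "Increase in the percentage of water consumed, 1 year after completing the interventions within each group relative to baseline". No other group enters the definition and no threshold is set.

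Section 15.0 tests the change separately in each group, by the Wilcoxon test: "The percentage of water consumed at baseline will be compared with that 1 year after finishing the intervention for each group". The Summary (Section 1.0) names only this test for follow-up data: "In each group, baseline water consumption will be compared with that 1 year after the end of the interventions using the Wilcoxon test".

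Section 15.0 then adds a comparison of the three groups at Time 3, by Friedman's test of related samples.

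The primary objective (Section 7.1) is to compare children who receive one, two or three interventions. The hypothesis (Section 8.0) is that the percentage of water is greatest with three.

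On conditions common to all groups, the Summary says "All schools will have water dispensers inside the classrooms". Section 12.4 starts free water access with the first session, which comes after the October 2017 baseline (Section 12.5). Time 3 is at the end of June.

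On group sizes, Section 13.0 gives Groups I and II one school of 81 first graders each. It then says "For Group III, the schools with the highest and lowest enrollments will be added", which makes 64 + 103 = 167.

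**The concern.** A before-after test asks whether consumption changed, not why. Three things besides education can move it here: water access that begins after baseline, the change of season between the two records, and ageing with secular drift over about 20, 32 and 44 months. The previous study (Section 4.5.2) shows that such movement occurs. Its controls had classroom water and bottles but no education, and the report reads "compared with the CG, which increased 37 mL". Of those controls, 95/364 = 26% met that study's effectiveness rule of more than 220 mL. The present definition asks only for an increase.

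Group size adds a second problem. A p-value from a before-after test depends on n as well as on the change. Group III has about twice as many children as either other group, and it is the group the hypothesis favours. If the three p-values are set side by side, significance in Group III alone can look like a dose-response when all groups have changed equally.

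**Working it through.** **The plan's own figure.** Section 13.0 uses d = 80.74 mL, SD = 399 mL, and 1.96 and 1.28 for alpha and beta:

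n = (1.96 + 1.28)² × 399² / 80.74² = 256.36, rounded up to 257.

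This reproduces. It is a one-sample (before-after) formula applied to all schools together, so 90% power refers to the pooled 257 and not to any single group.

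**Children per group after 28% loss.** 81 × 0.72 = 58.3, taken as 58. 167 × 0.72 = 120.2, taken as 120.

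**Power per group, normal approximation, same true change in all groups.** Power = Φ(d√n/SD − 1.96) + Φ(−d√n/SD − 1.96).

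- n = 58: 80.74 × √58 / 399 = 1.541, power 0.338.
- n = 120: 80.74 × √120 / 399 = 2.217, power 0.601.

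**Wilcoxon signed-rank test, simulated.** Changes are normal with SD 399, children are independent, the test is two-sided at 0.05, and the true change is the same in every group. Repeat runs differ by a point or two.

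| Common change | Group sizes | I | II | III | Only III | Only I |
|---|---|---|---|---|---|---|
| 0 mL | 58/58/120 | 5% | 5% | 5% | 4% | 4% |
| 37 mL | 58/58/120 | 10% | 10% | 17% | 13% | 8% |
| 80.74 mL | 58/58/120 | 31% | 31% | 57% | 27% | 9% |
| 80.74 mL | 79/79/79 | 40% | 40% | 41% | 15% | 14% |
| 167 mL | 58/58/120 | 86% | 86% | 99% | 2% | 0.1% |

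The 37 mL row is the earlier controls' drift with no education effect. The 167 mL row is the earlier intervention group's 8-month change. Both are reported as medians and are treated here as means.

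**Reading the table.**

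- With no change at all, each test keeps its 5%. Imbalance matters only when there is a common non-zero change.
- At 80.74 mL, imbalance raises the chance of Group III alone being significant from about 15% to 27%, an excess of about 12 points.
- With 37 mL of drift only, at least one group is significant in about 33% of trials, against 14% with no change. Equal groups give the same 33%, so that figure reflects drift and three tests, not unequal size.

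**School clustering.** The documents give no intraclass correlation. With assumed values of 0.01 to 0.05 for change and a common 80.74 mL, Groups I and II reach 34–45% and Group III 54–57%. The gap narrows but remains.

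**The case against.** **The plan does compare the groups.** Section 15.0 contains a three-group comparison, and Sections 7.1 and 8.0 are worded between groups. A reader might infer that the plan has no comparator anywhere, or that the hypothesis will be judged by which Wilcoxon test is significant. The documents support neither. What stands is narrower. Friedman's test needs related samples, whereas the three groups are different children. As planned it uses Time 3 values without baseline. Nothing says that it, and not the Wilcoxon tests, decides the conclusion, and the effectiveness definition points to the within-group change.

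**The size depends on the input.** Section 13.0 does not say whether 80.74 mL is a within-group change or a difference between arms. At 167 mL, the misleading pattern almost vanishes. This is correct, and 27% should be read as one point in a range.

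**A between-group contrast does not cure everything.** Season, dispensers and bottles are common to all groups, so they bias the before-after result more than the contrast. Age and calendar year are not common: Time 3 falls in June 2019, 2020 and 2021 for Groups I, II and III. Groups I and II are one school each, and Section 12.4 assigns schools by enrolment and teacher interest, not at random. A reader might infer that comparing groups removes all the listed confounding. It does not.

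**Per-child effectiveness.** If the yes/no variable is counted as a proportion of children, that proportion does not grow with group size, so the size argument applies only to the Wilcoxon p-values. The attribution problem applies to both.

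**Conclusion.** The point holds in this form. Followed as written, the effectiveness definition and the separate Wilcoxon tests would credit the education with change that it may not have caused. For any common non-zero change with the same SD, Group III is more likely to be significant because of its size alone.

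The direction is firm; the amount is not. The chance of Group III alone being significant, with no difference between groups, runs from about 2% (167 mL) to 27% (80.74 mL), and some of it would occur with equal groups. It would go too far to say that 27% is produced by sample size alone.

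The figures rest on normal changes in mL, SD 399 in every group, 28% loss in each group, independent children, and medians used as means. The tested outcome is a percentage, for which the documents give no effect or SD. The size and direction of any seasonal effect are also not given.

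**What to change.** - **Sections 14.0 and 15.0, and the Summary:** report within-group change descriptively (median change with 95% confidence interval per group). State that no claim of effectiveness rests on its p-values.
- **Section 15.0, three-group comparison:** replace Friedman's test with an independent-groups method that uses baseline. Options are Kruskal-Wallis on change in the percentage of water, or regression of the Time 3 percentage on group and baseline. Give pairwise group differences with confidence intervals, and state that conclusions on the number of interventions rest on these.
- **Limits to state with the result:** the contrast does not separate the number of interventions from school, or from age and calendar year at Time 3. Child-level p-values also ignore school clustering. With 58/58/120 children and equal true change, Kruskal-Wallis on change gives about 5% false positives if children are independent, but about 15%, 25% and 46% at assumed intraclass correlations of 0.01, 0.02 and 0.05. Results should therefore also be shown by school.

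**Cost.** Analysis wording only; the data collection is unchanged and no control arm is added. The sponsor gives up stand-alone within-group significance claims. The intervals will be wide. For Group III versus Group I in mL, the half-width is 1.96 × 399 × √(1/58 + 1/120) = 125 mL before any allowance for clustering, so the plan should expect limited precision on the number of interventions.
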